By completing specific objective #1, we will be fully prepared for TASKPEN pilot testing, having ready an adapted version of TASKPEN that includes all the essential implementation strategies necessary to overcome barriers to HIV-NCD integration in routine care settings. While the peripheral elements and implementation strategies used to introduce TASKPEN may undergo adaptation under specific objective #1, it is important to note that the 5 core, evidence-based components outlined in Table 1 and proposed for this pilot will not substantively change. Under specific objective #2, we will launch the TASKPEN pilot and fully task-shift our intervention to NPHWs and integrate it within the PEPFAR-supported HIV service delivery platform. Concurrently with implementation, during the pilot we will identify facilitators and barriers to TASKPEN introduction, assess preliminary implementation outcomes and patient and provider preferences related to integrated management of cardio-metabolic complications for PLHIV, ascertain early clinical outcomes for patients before and after TASKPEN piloting, and collect formative costing data.

b. Study design

For this objective, we will conduct a quasiexperimental "mini" cross-sectional stepped-wedge study at the 2 pilot sites employing a mixed methods approach. First, at the two pilot sites (i.e. A and B), we will conduct a baseline assessment of select outcomes for PLHIV receiving the existing standard of care. This will involve conducting a brief biobehavioural survey or "patient survey" among a consecutive sample of ~376 adult PLHIV presenting for routine HIV services at the two sites (i.e., ~188 PLHIV per site, see Sample Size and Statistical Power below). After this first patient survey, one randomly selected facility (i.e. cluster) will be switched to the full TASKPEN intervention. The patient survey will be repeated again with another ~376 adult PLHIV after ~3 months at both sites before switching the second site to the full TASKPEN intervention. After switching the second

Figure: Study schematic with "mini" stepped wedge and nested cohort.

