site, both pilot sites A and B will implement the full TASKPEN intervention for another ~3 months after which time a third and final "end line" patient survey will be conducted. Survey data will be used to estimate the pilot effect size of the TASKPEN intervention to aid in planning a future larger trial and to measure WHO PEN process indicators for all PLHIV in care who accessed routine health services during the pilot period.

Complementing the baseline, midline, and endline patient surveys will be a "nested cohort" of PLHIV with cardio-metabolic comorbidities enrolled at both sites beginning at baseline. At each site, we will enrol a subset of ~100 baseline survey participants (i.e., ~200 total) found to have at least one cardio-metabolic complication or risk factor (see below) on the baseline survey. We will then follow these nested cohort participants longitudinally for ~9 months at site A and site B. A nested cohort sample size

TASKPEN Study

of 200 PLHIV was selected to represent about 50% of all baseline survey participants who are estimated to have a cardiometabolic co-morbidity at each site (i.e., ~188 PLHIV in care per site who complete a baseline survey x ~50% of survey participants with hypertension, diabetes, and/or dyslipidaemia = ~100 participants per site), consistent with estimates for the prevalence of cardiometabolic comorbidities among PLHIV in Lusaka, Zambia. Moreover, the nested cohort sample size of ~200 total participants (~100 per site) is intended to assess the feasibility of the intervention and longitudinal follow up of study participants to inform a future larger trial; it is not intended to test a hypothesis *a priori*. By enrolling a nested cohort, we can use their data to enrich inferences made from the cross-sectional surveys and will be able to make more granular comparisons between and within sites (i.e. with an external and internal comparator group, respectively).

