The suggested sample size for DCE surveys is estimated by the method of Orme and Johnson as N >500c/(t x a), where c is the number of analysis cells (i.e., the largest number of levels for any attribute), t is the number of choice tasks, and a is the number of options. Assuming maximum 4 levels per attribute, 10 choice tasks, and 3 options, the minimum required sample size is 67 to examine the effects in the overall study population. However, a larger sample size is necessary to measure preference heterogeneity among patients participants. Thus, administering the DCE questionnaire to all nested cohort participants is being proposed to fully assess preference heterogeneity in the patient population.

For our qualitative and costing components, we have not calculated sample sizes *a priori*, as we will not be conducting statistical hypothesis testing. The total participants listed in Table 5 (below) are meant to serve as a guide only. Additional IDIs, FGDs/ implementation surveys, KIIs, and structured observations may be added until thematic saturation is reached and no new themes are elicited from participants.

vi. Recruitment & Enrolment

For the cross-sectional patient surveys, we will coordinate with facility staff to approach, in person, consecutive PLHIV accessing routine health services at the clinic about the study. We will sensitize patients about the study at the clinic appointment desk, triage, and other waiting areas to take advantage of times when patients are queueing or otherwise awaiting health services. We will seek to conduct study activities after patients have received most of their clinic services so as not interrupt routine work and patients flows. After written informed consent procedures are completed, we will request basic locator information (e.g. phone number) to follow up with participants and administer a brief, one-time bio-behavioral survey.

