Nested cohort participants will be the only study participants having more than one encounter with the study team. As such, we will schedule study follow-up visits approximately every 3 months over a ~9-month period starting at 2 weeks from the time of the baseline patient survey. Thus, their total engagement with the study will amount to about 4 follow-up visits (at ~2 weeks and then around 3 and 6 months from the baseline survey plus one study exit visit at around 9 months). Study visits will be largely aligned with the schedule of routine clinic visits stipulated in the Zambia national HIV guidelines (i.e., every 3-6 months for established ART patients and more frequently during the first month of treatment for new ART patients) and will be scheduled mostly for times when the study teams are conducting the midline and endline surveys at the study sites. Study research assistants, who are not

providing any interventions as part of TASKPEN, will contact the participants in the nested cohort via phone call every month to check vital and clinic status (still in care at original site) and ascertain any changes in household location. If the participant is unreachable, community tracing will be done to verify whereabouts leveraging existing CIDRZ community tracing platforms in Lusaka. At the next time a survey assessment is done at the site, and before the clinic is switched from control to intervention, the nested cohort participants will be re-assessed by the team.

Study follow-up procedures will be designed so as not to disrupt routine care delivery and will include: determination of retention in integrated HIV/NCD care and referral for routinely available adherence and psychosocial counselling and back-to-care services, as appropriate; lab monitoring for cardio-metabolic NCDs (see laboratory procedures below) if not already done by the government health workers during their routine health visits; brief survey administration to assess adherence, nutritional status, tobacco and alcohol use, and other NCD-related health parameters; and completion of the quality of life and DCE questionnaires.

e. Data collection plan and tools

Data collection overview

As in specific objective #1, data collection activities for specific objective #2 will involve a combination of NHSR and implementation research activities detailed below.

ii. Non-human subjects research activities

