At both sites, during a ~1-month "run in period," we will establish basic study infrastructure to enable quantitative data collection during the patient surveys. This will involve fully equipping study offices at the sites and ensuring information technology connectivity and available computer hardware. Then, study staff will begin data collection on cardio-metabolic and implementation outcomes of interest using three cross-sectional patient surveys. The first two surveys (at baseline [0 months] and midline [3 months] will be done immediately prior to a site switching to the intervention; a final survey will be done at 6 months and serve as the "endline" assessment. The surveys will ask questions about participant socio-demographics, HIV and cardio-metabolic NCD history, and health behaviours. It will involve trained study staff administering a tablet-based questionnaire to participants, as well as taking participants' anthropomorphic measurements (e.g., height, weight, and waste circumference), vital signs (e.g., pulse and blood pressure), and a small blood sample to measure random/ fasting blood glucose, haemoglobin A1c, cholesterol levels, and other biomarkers. These laboratory tests will follow MOH recommendations and may include new point-of-care diagnostic technologies (see laboratory procedures section), and the results will be reported to patients and the clinic for clinical management. Any participant found to have newly diagnosed hypertension, diabetes/ pre-diabetes, and/or dyslipidaemia will be linked to care at the study sites. In addition, the study QA/QC nurse and study clinical scientist/ doctor will be available to act immediately on any vital sign or laboratory abnormality, including to offer patient counselling, provide warm "handoffs" to clinical staff, refer patients for acute care at the study sites, and prescribe appropriate outpatient treatment for non-acute issues in cases where MOH staff are not available (e.g., after business hours). Finally, we will ask participants to provide a phone number so we can invite those identified with hypertension, diabetes/ pre-diabetes, and/or dyslipidaemia through the survey to be followed in the nested cohort.

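### Two of the three intervention survey cells fall only about 3 months after the switch, so an effect that grows with exposure would be under-estimated, and the plan describes no way to see this

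*Combined protocol and SAP*

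**What the plan says.** All references are to the combined protocol and SAP, section 8, Specific Objective #2. Site A here means the site randomised to switch first.

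- **Survey timing (e.iii, Quantitative research data collection).** The baseline (0 months) and midline (3 months) surveys "will be done immediately prior to a site switching to the intervention", and the endline survey is at 6 months.
- **Switches (b, Study design).** "The patient survey will be repeated again with another ~376 adult PLHIV after ~3 months at both sites before switching the second site". After that, "both pilot sites A and B will implement the full TASKPEN intervention for another ~3 months" before endline.
- **Visit schedule (d.vii, Nested cohort follow-up procedures).** Routine HIV visits are "every 3-6 months for established ART patients and more frequently during the first month of treatment for new ART patients".
- **Recruitment (d.vi).** The surveys approach "consecutive PLHIV accessing routine health services at the clinic", preferably once most of that day's services have been delivered. Eligibility (d.ii) is any adult seeking routine HIV care at the site. Documented exposure to TASKPEN is required only for the in-depth interviews.
- **Analysis (g.i).** Dual HIV/NCD control is compared between control and intervention periods in a mixed logistic model, with facility random and time fixed. No term for exposure or time since switch is described.
- **Use.** The survey data are to give the pilot effect size for planning the larger trial (b), and the preliminary effect is among the primary measures (e.vii).

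**The concern.** A patient surveyed at the first visit after the switch has had, at most, that day's TASKPEN care. Treatment begun that day cannot have changed that day's blood pressure, HbA1c or lipids. The HIV component uses the most recent viral load, which may predate the switch.

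In two of the three intervention cells, the time since the switch is about equal to the shortest routine interval for established patients. All three cells are nonetheless coded as fully treated. The protocol allows for build-up elsewhere: structured observations wait until the intervention is at steady state (e.ii). The surveys that supply the effect estimate have no such allowance. The run-in of about 1 month comes before baseline and sets up study infrastructure, so it is not a post-switch lag.

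At stake is how the pilot estimate is read. Without data on prior exposure, a null or reversed result could not be told apart from patients not yet having received the programme, and it would feed into planning the larger trial.

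**Working it through.** **Inputs from the documents.** 2 sites, 3 surveys, 188 per site per survey; proportions 0.60 and 0.75; ICC 0.25; two-sided alpha 0.05; stated power 80% (d.v). Visit intervals and survey times are as quoted above.

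**Step 1: reproduce the stated power.** Total variance is 0.6 × 0.4 = 0.24. With ICC 0.25, the between-site part is 0.06 and the residual part 0.18, or 0.18/188 per cell. The Hussey-Hughes stepped-wedge variance gives SE = 0.0535. Then 0.15/0.0535 = 2.80, 2.80 − 1.96 = 0.84, and power is 80%. The stated figure reproduces. It assumes the full 0.15 in every intervention cell.

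**Step 2: time since switch.**

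| Intervention cell | Nominal n | Months since switch |
|---|---|---|
| Site A midline | 188 | about 3 |
| Site A endline | 188 | about 6 |
| Site B endline | 188 | about 3 |

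The two early cells hold 2 × 188 = 376 of 3 × 188 = 564, or 67%.

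**Step 3: share at a first post-switch visit.** On the nominal schedule everyone in the two early cells is at a first visit, which gives 67% overall (more if some patients attend exactly 6-monthly). The figure is sensitive at the 3-month edge. The table assumes a 1-month survey window, visit-timing SD of 0.25 month, and attenders sampled in proportion to visit frequency. None of these figures is in the documents.

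| Visit mix | Window before the mark | Centred | Midline before, endline after | After the mark |
|---|---|---|---|---|
| Even over 3–6 months | 70% | 63% | 59% | 52% |
| Half 3-, half 6-monthly | 72% | 49% | 45% | 27% |
| All 3-monthly | 59% | 32% | 33% | 6% |
| All 6-monthly | 97% | 83% | 70% | 70% |

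**Step 4: what the model estimates.** Let D1, D2 and D3 be site A minus site B at the three surveys. On the linear scale the estimate is D2 − (D1 + D3)/2. The weights on the intervention cells are +1 (A midline), −0.5 (A endline) and +0.5 (B endline). With a random site effect at ICC 0.25 the halves become 0.496. With e3 and e6 for the effects at 3 and 6 months:

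estimate ≈ e3 − 0.5·e6 + 0.5·e3 = 1.5·e3 − 0.5·e6

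The cell with the longest exposure enters negatively. Setting e6 to the planned 0.15, with e3 assumed, and power = Φ(d/SE − 1.96) + Φ(−d/SE − 1.96):

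| e3 | 1.5·e3 − 0.5 × 0.15 | Power |
|---|---|---|
| 0.15 | 0.150 | 80% |
| 0.10 | 0.075 | 29% |
| 0.075 | 0.038 | about 11% |
| 0.05 | 0.000 | null |
| 0 | −0.075 | wrong sign |

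**Step 5: precision of an exposure-coded analysis.** Suppose the exposed shares are 25%, 75% and 25% (A midline, A endline, B endline). The A-minus-B exposure differences are then 0, 0.25 and 0.50, with sum of squares about their mean 0.0625 + 0 + 0.0625 = 0.125. For 0/1 coding the differences are 0, 1 and 0, with sum of squares 0.667. The SE ratio is √(0.667/0.125) = 2.3, so the SE rises from about 0.054 to 0.123. Power for 0.15 is Φ(0.15/0.123 − 1.96), about 23%.

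**The case against.** Several points against the concern have force.

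- **Most intervention participants unexposed?** A reader might infer this, but the documents do not establish it. They give neither the visit mix nor the survey window, and the midline and endline wording allows fieldwork to run past month 3. Step 3 then gives first-visit shares as low as 27% for a half-and-half mix and 6% if all are 3-monthly. The 3 to 6 months is also the HIV schedule. Some hypertension care runs through the outpatient department, and patients with uncontrolled disease may attend sooner.
- **Exposure not recorded at all?** This cannot be verified. The instruments are in an appendix not included here. The survey covers HIV and NCD history, and pharmacy records are reviewed for survey participants. The supportable statement is that the plan describes no exposure variable.
- **Must the surveys be moved?** No. Surveys at, for example, 4.5 and 9 months would still leave 6-monthly patients at their first visit in both early cells. With a half-and-half mix, exposure would be 50/100/50%, and the model would return 1.5 × 0.075 − 0.5 × 0.15 = about 0.04.
- **A pilot with a legitimate roll-out estimand.** Coding by site period is a proper choice, the effect is called preliminary, and the nested cohort follows patients for about 9 months (about 9 months after the switch at site A and 6 at site B).

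These points limit the size of the problem and the remedy. They leave the timing of the two early cells, the negative weight on the later one, and the absence of any described exposure criterion or term.

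**Conclusion.** The concern holds in a limited form, as something that should be fixed. In two of the three intervention cells, the survey comes about 3 months after the switch, when patients on 3- to 6-monthly visits may be at their first post-switch visit. If the effect grows with exposure, the planned model under-estimates it. The estimate equals e3 − 0.5·(e6 − e3), so it falls below even the 3-month effect. With 0.075 at 3 months and 0.15 at 6 months it is about 0.04. It is null when e3 is one third of e6, and negative below that.

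This rests on a linear approximation to the planned logistic model, on effects that depend only on time since switch, and on assumed values of e3. If the full effect is present by 3 months there is no bias. The documents do not support a prediction that the pilot will report no effect.

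**What to change.** 1. For every survey participant, record the date of the previous clinic visit and whether it followed that site's switch. Report the exposed share in each site-by-survey cell.
2. Describe the 0/1 result as the effect of about 3 months of site roll-out, not as the effect of receiving TASKPEN or as the effect size for the larger trial. State that it falls below the 3-month effect if the effect is still growing.
3. Add a supplementary analysis coded by exposed share or by time since switch. State in advance that it is imprecise (Step 5), and read it alongside the nested cohort's longer follow-up.

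The cost is two fields, which can draw on records already reviewed for survey participants, plus analysis-plan wording. If the appendix instruments already capture the previous visit, only the reporting and wording are new. The survey dates need not change.
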